feasible, we propose a pseudorandom ternary sequence approach to frequency distribution during disparity driven vergence to allow rapid analysis over a wide range of frequencies. Essentially, a pseudorandom frequency distribution can help extrapolate data to a larger frequency data set. We will also be evaluating the safety and side effect profile of using the goggles using a medical symptom questionnaire.

5) **Inclusion and Exclusion Criteria**

Inclusion:

- Aged 18 or older
- Both females and males

Exclusion:

- Central processing disorder
- Impaired vision without corrective lenses (max 20/60 uncorrected)
- Moderate to severe hearing loss (>55dB PTA, <50% word identification)
- Vestibular disorder except for patients recruited for SA3
- History of ear surgery other than myringotomy with or without tube placement
- Pregnant women
- Prisoners
- Adults unable to consent

6) **Number of Subjects**

60 subjects – 30 normal controls (no mTBI), 30 patients with mTBI.

7) **Recruitment Methods**

Normal subjects will be recruited from a pool of patients from a population who are unaffiliated or affiliated with University of Miami and meet inclusion criteria and not excluded by exclusion criteria. The faculty and students of any University of Miami School will be recruited through advertising in e-mails. Emails will be sent to staff and faculty associated with the UM Clinical Research Building (CRB) that have their emails stored in the UM Outlook server. Subjects will not be paid to participate. Students and staff will be assured that their participation will have no effect on their school performance or grades.

8) mTBI patients will be recruited by convenience from a pool of patients with history of mTBI and no prior vestibular disorders that present to the UM CRB Otology Clinic of [name] (SA3)”. The determination of their fitness for participation will be made during [name] clinical history and physical by asking about the history of the head injury and past medical history.

9) **Study Timelines**

Vestibular tests will take 15 minutes.

10) **Study Endpoints**

Each participant’s study will be completed when they have completed the vergence testing and other vestibular tests. At that point, the data will be de- identified.

11) **Procedures Involved**

The study will be conducted in 2 phases in which each phase comprises of thirty participants.

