In the first phase, thirty participants without mTBI who meet the inclusion criteria and are not excluded will be chosen to participate. Participants will sign an informed consent document and undergo 1 session of vergence testing, along with a series of vestibular tests. After this testing, the data will be de-identified and will only be labeled with sex and age of patient.

In the second phase, thirty participants with mTBI who meet inclusion criteria and are not excluded will be chosen to participate. Participants will sign an informed consent document and undergo 1 session of vergence testing, along with a series of vestibular tests. After this testing the data will be de-identified and will only be labeled with sex and age of patient.

After the session, patients will be given a medical symptom/toxicity questionnaire (MSQ) to evaluate for any side effects.and the SCAT-5 questionnaire, which will evaluate their current symptoms.

For each vestibular test and data to be obtained, see table below:

Test	Activity	Outcome OR Ordinal Value
Vergence Pursuit	Focusing on object moving forward and backwards	0 - 100
Spontaneous Nystagmus	Focusing on an object	Normal / Abnormal (Side)
Saccades ~ Horizontal Random	Focusing on objects randomly in horizontal axis	Normal / Abnormal (Side)
Saccades ~ Vertical Random	Focusing on objects randomly in vertical axis	Normal / Abnormal (Side)
Smooth Pursuit Horizontal ~ 0.1 Hz	Tracking objects in horizontal axis, at 0.1 Hz	Normal / Abnormal (Side)
Smooth Pursuit Horizontal ~0.75 Hz	Tracking objects in horizontal axis, at 0.75 Hz	Normal / Abnormal (Side)
Smooth Pursuit Vertical ~0.1 Hz	Tracking objects in vertical axis, at 0.1 Hz	Normal / Abnormal (Side)

Smooth Pursuit Vertical ~0.75Hz	Tracking objects in vertical axis, at 0.75 Hz	Normal / Abnormal (Side)
Predictive Saccades	Tracking an object moving in predictable manner	Percent (%) Error
Antisaccade	Moving eyes away from visual onset	% Error
OKN (optokinetic nystagmus) Trapezoidal	Tracking moving field	Normal / Abnormal (Side)
Visual Reaction Time	Reaction time to object	Seconds
Saccades and Reaction Time	Reaction time to off-center object	Seconds
Auditory Reaction Time	Reaction time to sound	Seconds
Self-Paced Saccade	Saccadic motion between two fixed targets	0 - 100
Pupil Reflex	Normal light reflex	0 - 100
Subjective Visual Vertical	Ability to perceive subjective tilt	0 - 100

12) **Data Storage**

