The only data to be stored will be the results of the vergence tests and vestibular testing done during the two sessions. These results will be tied together by a subject number that will also link to the sex of the patient and age of the patient. No PHI that identifies any participant will be kept. All the previously described data will be stored on the PI's computer and used for analyses purposes in room 580 of the clinical research building at the University of Miami Medical Center located at [name]. It will be password protected, and unique identifiers used for subject protection. Data will not be distributed, except in the form of peer-reviewed publication or oral presentation maintain the confidentiality of the subjects.

13) **Data Management***

Group mean data and single subject design will be utilized. In the group mean data scoring on each of the sessions will be aggregated for each of the specific aims. First session scores will be compared to second session scores using standard statistical methods with significance defined as $p < 0.05$. For the single subject design the number of subjects for each vestibular tests for each aim who have a significant difference in scores between the first and second session will be calculated and analyzed with descriptive statistics. In this way the investigators can calculate the difference between each test on the two sessions for each protocol, as it is very possible that some tests may be significantly different between the sessions and some tests will not.

Data will be stored on the PI's computer and used for analyses purposes in room 580 of the clinical research building at the University of Miami Medical Center located at [name]. It will be password protected, and unique identifiers used for subject protection. Data will not be distributed, except in the form of peer-reviewed publication or oral presentation maintain the confidentiality of the subjects. . No PHI that can identify any subjects will be kept beyond the second session of testing.

14) **Withdrawal of Subjects**

Subjects can withdraw at any time but if they withdraw their data will not be used and they will be replaced in the study by a new subject.

15) **Risks to Subjects**

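### The single-subject rule in Section 13 cannot be carried out as written: one session is scheduled, significance for one person is undefined, and no within-person error is supplied

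*Combined protocol and SAP*

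**What the plan says.** Section 13 (Data Management) describes two analyses. The first is a group comparison of first-session with second-session scores, judged at p < 0.05 by unspecified standard methods. The second is a single-subject analysis, which counts "the number of subjects for each vestibular tests for each aim who have a significant difference in scores between the first and second session". That count is to be summarised descriptively only. The 0.05 level is attached to the group comparison. No criterion is given for an individual.

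On the number of sessions the document disagrees with itself. In Section 11 (Procedures Involved), participants in each phase "undergo 1 session of vergence testing, along with a series of vestibular tests". Section 12 (Data Storage) refers to "vestibular testing done during the two sessions", and Section 13 builds its analysis on two.

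The Section 11 table lists 17 tests with one outcome type each. Eight are recorded as "Normal / Abnormal (Side)". The other nine are numeric. Section 6 sets the size: "60 subjects – 30 normal controls (no mTBI), 30 patients with mTBI".

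**The concern.** Calling one person's change significant requires a measure of how much that person's score varies when nothing has changed. The plan gives no measurement error, test-retest SD, reliable-change threshold or number of repeat trials. It also gives no second session in the procedures. Whoever runs the analysis would have to invent the rule, possibly after seeing the data.

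The title presents the test as potentially diagnostic, and SA3 compares mTBI subjects with normal subjects. Individual results are therefore of real interest, and the single-subject count is the analysis aimed at them. As it stands it gives no individual result for SA3. If the gap is filled informally, a handful of flags would appear by chance on most tests, with nothing in the plan to set them against.

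**Working it through.** The plan states no power, effect size, SD or expected count, so it has no figure to reproduce beyond 30 + 30 = 60.

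**Inputs**
- Group size 30 (Section 6).
- Table rows (Section 11): 8 Normal/Abnormal, 4 on a 0-100 scale, 2 percent error, 3 in seconds. 8 + 4 + 2 + 3 = 17, of which 9 are numeric.
- Assumption: a two-sided 5% level for each individual, carried over from the group comparison.

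**Step 1. One person's own data.** One score in each of two sessions gives one difference. The degrees of freedom for its variance are 1 - 1 = 0, so no p-value follows from those two values alone.

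**Step 2. Normal/Abnormal tests.** The exact McNemar test on one changed pair has p = min(1, 2 x 0.5) = 1.0. An unchanged pair carries no evidence of change. So p < 0.05 cannot be reached on 8 of the 17 tests.

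**Step 3. Numeric tests with two sessions and a borrowed error term.** A count then becomes possible, but it depends on the source of the error.
- *SD of the 30 differences.* Suppose a person is flagged when the difference lies more than 1.96 SD from the mean difference. The squared deviations sum to 29 SD², so the number flagged must be below 29 / 1.96² = 7.55, that is, at most 7 of 30. In simulation the rule flags about 1.3 of 30 on average, whether nobody changes or everyone shifts by six standard errors of measurement (SEM). It can be computed but does not detect a shared change.
- *Stated SEM.* Flag when |difference| > 1.96 x √2 x SEM. If the true SEM is 0.75, 1, 1.25, 1.5 or 2 times the assumed one, the expected false flags per test are 0.3, 1.5, 3.5, 5.7 or 9.8 of 30. These ratios are assumptions, chosen to show the range.

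**Step 4. Chance expectation under any valid 5% rule.** 30 x 0.05 = 1.5 per test per group; over the nine numeric tests, 9 x 1.5 = 13.5.

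**Step 5. A rule that needs only one session.** Compare each mTBI subject with the controls. The cut-off is t(29 df, 0.975) x √(1 + 1/30) = 2.045 x 1.0166 = 2.08 control SD.

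All 30 mTBI subjects are judged against the same estimated control mean and SD, so their flags are correlated and the binomial tail does not apply. The table compares the two under no group difference. The simulation used normal scores, 30 controls, 30 patients and 400,000 runs.

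| Flags among 30, one test | Binomial (independent) | Shared control sample |
|---|---|---|
| Mean | 1.5 | 1.5 |
| P(at least 1) | 0.785 | 0.70 |
| P(at least 4) | 0.061 | 0.10 |
| P(at least 5) | 0.016 | 0.047 |

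These are per-test probabilities. If the nine numeric tests were independent (an assumption), the chance that at least one of them reached five flags would be 1 - (1 - 0.047)⁹ = 0.35.

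**The case against.** The strongest reply is that the analysis is under-described rather than impossible. With 30 people tested twice, measurement error for the nine numeric tests could be estimated from the group's differences or taken from an outside source. The table column gives the scale of each outcome, not how many measurements lie behind it. The two percent-error outcomes imply several trials, which could supply within-person error if trial data were kept. All of this stands. A reader might infer that the count could not be computed even with two sessions, or that no chance benchmark could exist. The documents support neither. The error term is unspecified for the numeric tests, and the benchmark is omitted but follows once a valid rule is set.

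A second reply is that the problem reduces to the session contradiction, since the sentence falls away if one session is intended. That is partly right, but settling on two sessions would leave individual significance undefined and the eight Normal/Abnormal tests without any route to it.

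A third is that a comparison with controls answers a different question from change between sessions. That also stands: it serves SA3 and does not replace retest change for SA1 or SA2. Finally, nothing in Section 13 says the count will be read as individual abnormality. That is a risk of leaving the rule open, not a stated intention.

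**Conclusion.** The point holds in this form: the Section 13 single-subject rule cannot be carried out as written and yields no individual result for SA3. Three gaps cause this: only one session in the procedures, no definition of individual significance, and no within-person error in the data as described. For 8 of 17 tests individual significance is out of reach even with two sessions. For the other 9 it would need a borrowed error term that the plan does not name, and the choice matters: false flags run from 0.3 to 9.8 of 30 per test over the range of SEM ratios tried.

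A reader might take five or more flags of 30 as strong evidence, from the binomial 0.016. For a comparison with a shared control sample the figure is 0.047 per test, with no allowance for the number of tests, so that threshold is weak.

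The conclusion assumes one recorded value per test per session, which is inferred from the table, and a two-sided 5% individual level. The simulated probabilities also assume normal scores.

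**What to change.** 1. Reconcile Section 11 (one session) with Sections 12 and 13 (two sessions).
2. For SA3, replace the single-subject sentences in Section 13 with a single-case comparison on the nine numeric tests: flag an mTBI subject when |score - control mean| exceeds 2.08 control SD. Where bounded or skewed scores make normality doubtful, specify a control percentile or a transformed score in advance.
3. Report the count out of 30 beside the chance expectation of 1.5 per test, with a reference distribution simulated to allow for the shared control sample. State that it is per test, with no multiplicity allowance.
4. For the eight Normal/Abnormal tests, report the proportion abnormal in each group.
5. If two sessions are kept for SA1 or SA2, pre-specify a reliable-change threshold for the numeric tests and name the source of its measurement error.

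The cost is a few sentences in Section 13 and a short simulation. The SA3 comparison needs no new data. Its limits are that it relies on a distributional assumption and addresses SA3 only.

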*Examining disparity driven vergence as a potential
diagnostic test for mild traumatic brain injury (mTBI)*

NCT Number NCT03529799

1) **Protocol Title**

Examining disparity driven vergence as a potential diagnostic test for mild traumatic brain injury (mTBI)

2) **IRB Review History***

None.

3) **Objectives***

Specific Aim 1 (SA1): Determine the validity and safety of disparity driven vergence testing with a portable goggle system using a pseudorandom ternary sequence of frequencies on a group of normal subjects.

Specific Aim 2 (SA2): Determine the vergence testing control values using a portable goggle system using a pseudorandom ternary sequence of frequencies on a group of normal subjects.

Specific Aim 3 (SA3): Determine the vergence testing values with a portable goggle system using a pseudorandom ternary sequence of frequencies on a group of subjects with history of mild traumatic brain injury and compare this to values in normal subjects.

4) **Background**

Vergence eye movements for focusing on objects include either convergence, the coordinated movement of both eyes towards the midline, or divergence, the coordination movement of both eyes towards the periphery. These eye movements are thought to be controlled by complex neurophysiological mechanisms that can be susceptible to damage by traumatic brain injury. Known involved areas in vergence include the oculomotor nucleus, cerebellum, and visual association cortex (Conn 2016), all of which can sustain damage during head trauma.

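### Section 13 applies an unadjusted p < 0.05 test by test to a 17-test battery with no primary outcome named, so the chance of at least one false-positive test is well above 5%

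*Combined protocol and SAP*

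**What the plan says.** Section 13 (Data Management) holds the only inferential rule: "First session scores will be compared to second session scores using standard statistical methods with significance defined as $p < 0.05". The rule is read one test at a time: "In this way the investigators can calculate the difference between each test on the two sessions for each protocol", with the expectation that "it is very possible that some tests may be significantly different between the sessions and some tests will not".

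The tests are those in Section 11 (Procedures Involved), introduced by "For each vestibular test and data to be obtained, see table below". The table has 17 rows, from Vergence Pursuit to Subjective Visual Vertical.

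Section 10 (Study Endpoints) names no outcome variable. It says only that each participant's "study will be completed when they have completed the vergence testing and other vestibular tests".

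The title and the three aims in Section 3 are about vergence. Aim 3 is to obtain vergence values in people with a history of mTBI and "compare this to values in normal subjects". Section 6 gives the sample as "30 normal controls (no mTBI), 30 patients with mTBI". No section sets out a test hierarchy, a multiplicity adjustment, an exploratory label or a rationale for the sample size.

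**The concern.** With 17 tests each judged at 0.05 and none designated in advance, the plan offers many chances of a significant result and no rule for which one answers the study question. Suppose vergence shows no difference and antisaccade error gives p = 0.03. Nothing in the plan says whether that is a positive study, a secondary signal or noise.

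The same freedom exists within vergence. Section 4 proposes a ternary sequence covering many frequencies, whereas the Section 11 table has one vergence row scored 0 to 100. The plan does not say which summary of the sequence is to be compared, so one of several could be chosen after the data are seen.

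At stake is how a published claim about a potential diagnostic test can be read. A chance-positive result could be given the prominence of a planned one.

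**Working it through.** The documents give no familywise error rate, power or effect size, so there is no figure of the plan's own to reproduce.

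**Inputs from the documents**
- Threshold: 0.05 per test (Section 13). Sidedness is not stated; two-sided is assumed.
- Number of tests: 17 (Section 11 table). Eight are Normal/Abnormal: spontaneous nystagmus, two random-saccade rows, four smooth-pursuit rows and optokinetic nystagmus. Nine are numeric: 0 to 100, percent error or seconds.
- Group sizes: 30 and 30 (Section 6).

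**Assumptions, because the documents are silent**
- No true difference on any test.
- The correlation between tests, the rate of abnormal results and the choice of test for the Normal/Abnormal rows are varied below.

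**Step 1: independent tests, each of exact size 0.05**

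1 − 0.95^17 = 0.582. The 50% line is crossed at 14 tests: 1 − 0.95^13 = 0.487 and 1 − 0.95^14 = 0.512. The expected number of false positives is 17 × 0.05 = 0.85. This is also the upper bound on the chance of at least one, whatever the dependence.

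**Step 2: correlated tests**

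For 17 two-sided z-tests with common correlation ρ, integrate over the shared factor x ~ N(0,1):

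1 − E{ [Φ((1.96 − √ρ·x)/√(1−ρ)) − Φ((−1.96 − √ρ·x)/√(1−ρ))]^17 }

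| ρ | Chance of at least one p < 0.05 |
|---|---|
| 0 | 0.582 |
| 0.1 | 0.569 |
| 0.2 | 0.537 |
| 0.25 | 0.516 |
| 0.3 | 0.493 |
| 0.5 | 0.386 |
| 0.7 | 0.271 |
| 0.9 | 0.149 |

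**Step 3: actual size of the tests on the eight Normal/Abnormal rows**

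With 30 v 30, the true size s of the chosen test was computed by enumerating the binomial outcomes. The familywise figure is then 1 − 0.95^9 × (1 − s)^8, with independence assumed.

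| Assumed abnormal rate | Fisher's exact | Uncorrected chi-square |
|---|---|---|
| 2% | 0.370 | 0.386 |
| 5% | 0.377 | 0.499 |
| 10% | 0.416 | 0.597 |
| 20% | 0.474 | 0.578 |
| 30% | 0.490 | 0.577 |
| 50% | 0.495 | 0.589 |

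The nine numeric tests alone give 1 − 0.95^9 = 0.370.

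**Step 4: what adjustment would do**

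Bonferroni over 17 uses 0.05/17 = 0.00294 per test. Under independence the familywise error is then 1 − (1 − 0.00294)^17 = 0.0488. One pre-named test at 0.05 has error 0.05 however many other tests are run.

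**Step 5: power cost of Holm over the other 16 tests**

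The first step is 0.05/16 = 0.0031. For a two-sample t-test at 30 v 30 with 80% power, the detectable standardised difference is 0.736 at 0.05 and 1.019 at 0.05/16. This applies to the eight numeric secondaries only.

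**The case against.** The strongest reply is that the vergence question is clear from the title and aims, that Section 10 itself mentions vergence separately from the other tests, and that this is a small, minimal-risk, convenience-sample study in which strict error control over a battery is unnecessary. Much of this stands. The documents do point to vergence as the subject. What they lack is a formal primary designation and a stated vergence summary. Requiring adjustment of all 16 other tests would indeed be a preference, since labelling them exploratory is enough. But the protocol does not call itself exploratory, and it sets a significance threshold.

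The p < 0.05 rule is also attached to a comparison of two sessions, while Section 11 gives each participant one session. As written, that comparison cannot be made within a person, and Section 13 states no test for the mTBI-versus-normal comparison of Aim 3. This objection is correct, and it means that the family of tests is itself poorly defined. It does not remove the concern: whichever comparison is intended, the only stated rule is an unadjusted 0.05 for each test.

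Three stronger readings might be inferred, and the documents do not support them:
- *A false positive is more likely than not.* This needs near-independence and tests of close to exact size. The battery is run on the same people and contains related sets of pursuit, saccade and reaction-time measures. A common correlation of about 0.3, or Fisher's exact test on the Normal/Abnormal rows, brings the figure below 50%.
- *The family is 51 tests, 17 for each of three aims.* The wording about each test for each aim belongs to the single-subject analysis, which is descriptive. Aims 1 and 2 both concern normal subjects, apparently the same group, and offer no group comparison.
- *The vergence test loses its 5% error.* A single pre-named vergence test keeps it.

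**Conclusion.** The concern holds in this form: an unadjusted 0.05 is applied test by test to 17 tests with no named primary outcome, so the chance of at least one false-positive test is well above the nominal 5%. It is up to about 58% under independence with exact size, about 49% at a common correlation of 0.3, 39% at 0.5 and 27% at 0.7, and 37% to 50% with Fisher's exact test on the eight Normal/Abnormal rows. An uncorrected chi-square test could take it to about 60%, because its size can slightly exceed 0.05.

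All these figures assume no true differences. The correlations, abnormal rates and test choice are assumptions that the documents do not settle, so the range matters more than any one value. The practical risk is selective emphasis on a chance-positive non-vergence test, or on one of several vergence summaries.

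**What to change.** - **Section 10:** name one primary outcome, the mTBI-versus-control difference in one pre-stated summary of the vergence response, tested once at two-sided 0.05.
- **Section 13:** replace the session comparison with this group comparison for Aim 3, and reconcile the section with the single session described in Section 11. Adding an adjustment to the present text would not be enough, because that text does not contain the Aim 3 comparison.
- **Other 16 tests:** label them exploratory, or Holm-adjust them if any are to be claimed as significant.
- **Several frequencies:** if vergence is analysed at more than one frequency, use one overall group-by-frequency test instead of a test at each frequency.

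The cost is protocol wording, and the primary vergence test loses no power. If Holm is chosen, the numeric secondaries lose power at the first step: the detectable standardised difference rises from about 0.74 to about 1.02. That figure does not apply to the eight Normal/Abnormal tests.

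### Section 14 discards and replaces withdrawn subjects even when their vergence recording is complete, so SA2 and SA3 rest on completers only and non-completion need not be reported

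*Combined protocol and SAP*

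**What the plan says.** Four parts of the combined protocol and SAP bear on this.

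- **Section 14 (Withdrawal of Subjects)** sets the rule: "Subjects can withdraw at any time but if they withdraw their data will not be used and they will be replaced in the study by"; the replacement is someone new. The exclusion covers all of the subject's data. Withdrawal is not defined, and no record of the number, timing or reasons is required.
- **Section 10 (Study Endpoints):** "Each participant’s study will be completed when they have completed the vergence testing and other vestibular tests". Section 11 lists 17 tests, of which Vergence Pursuit is the first row. It does not say that the tests are run in that order.
- **Section 6 (Number of Subjects):** "60 subjects – 30 normal controls (no mTBI), 30 patients with mTBI". Replacement refills each group to 30.
- **Section 3 (Objectives):** SA2 is to establish control vergence values. SA3 is to obtain vergence values "on a group of subjects with history of mild traumatic brain injury and compare this to values in normal subjects".

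Section 12 limits stored data to the vergence and vestibular test results, linked to a subject number, sex and age. Nothing elsewhere in the document softens the rule in Section 14.

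**The concern.** Suppose a subject completes the vergence test, has had enough during a later saccade or optokinetic task, and withdraws. Under Section 14 a valid vergence result is thrown away for a reason that has nothing to do with its quality. The replacement is, by construction, someone who got through the whole battery.

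For a normative sample (SA2) and a group comparison (SA3), this means that the values describe people who complete the battery, not people who present for testing. The rule is the same in both groups, but its effect need not be. If mTBI patients stop more often, and those who stop have worse vergence, the mTBI mean moves toward the control mean.

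The study also asks whether vergence could serve as a diagnostic test, and for that purpose the proportion of patients who cannot complete the test is a result in itself. As written, a report could show 30 of 30 in each group without saying how many people it took to get there.

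Because withdrawal is undefined, two members of the study team could handle the same early stop differently, one keeping the recording and the other discarding it.

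**Working it through.** **The plan's own figures.** The only relevant figure is 60 subjects, 30 per group. No effect size, SD, power or withdrawal rate accompanies it, so there is no derivation to reproduce.

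**Reading the sections together.** Section 10 defines completion as vergence plus the other tests, Section 14 removes and replaces those who withdraw, and Section 6 fixes 30 per group. It follows that each analysed group excludes everyone who withdrew, and that vergence data recorded before withdrawal are lost. This step needs no assumption about rates.

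**Possible size of the bias.** Everything here is assumed, because the documents give no inputs:

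- a fraction w of mTBI subjects, those with the lowest tolerance of the battery, withdraw and are replaced;
- tolerance is normally distributed, and low tolerance has correlation r with the vergence deficit;
- there is no selection in controls.

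The completers' mean deficit then falls by r × φ(z) / (1 − w) SD, where z is the upper-w normal quantile. The multiplier φ(z) / (1 − w) is:

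- w = 3%: 0.0680 / 0.97 = 0.070
- w = 5%: 0.1031 / 0.95 = 0.109
- w = 10%: 0.1755 / 0.90 = 0.195
- w = 20%: 0.2800 / 0.80 = 0.350

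Shift in SD units, with the number who must enter to give 30 completers, 30 / (1 − w):

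| w | r = 0 | r = 0.3 | r = 0.5 | r = 0.7 | r = 0.8 | Entered for 30 completers |
|---|---|---|---|---|---|---|
| 0% | 0 | 0 | 0 | 0 | 0 | 30 |
| 3% | 0 | 0.021 | 0.035 | 0.049 | 0.056 | 30.9 |
| 5% | 0 | 0.033 | 0.054 | 0.076 | 0.087 | 31.6 |
| 10% | 0 | 0.058 | 0.097 | 0.136 | 0.156 | 33.3 |
| 20% | 0 | 0.105 | 0.175 | 0.245 | 0.280 | 37.5 |

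At 3 to 5% withdrawal the shift stays below 0.08 SD if r is at most 0.7, and reaches 0.087 SD at r = 0.8.

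**Effect on power.** Section 13 gives a 0.05 threshold but attaches it to a comparison of first and second sessions. I assume two-sided 0.05 for the group comparison. With 30 per group, the difference detectable with 80% power is (1.960 + 0.842) × √(2/30) = 0.72 SD. If the true difference were that size, selection in the mTBI group alone, allowing for the slightly smaller SD among completers, would lower power from 80% to:

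- 73–77% at w = 5%
- 65–74% at w = 10%
- 50–68% at w = 20%

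In each range the lower figure is for r = 0.7 and the higher for r = 0.3.

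**What the model does not separate.** The shift combines subjects who finished vergence before stopping with those who did not. Retaining data recovers only the first group, and the split cannot be estimated because the testing order is not stated.

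**The case against.** The strongest reply is that the effect may be negligible or absent. Section 9 states: "Vestibular tests will take 15 minutes". Section 15 describes the risks as minimal. Few people may withdraw from so short a session, and with no withdrawals there is no bias. Similar selection among controls would partly cancel any shift in the SA3 contrast. All of this stands, and it is why the size is given as a range starting at zero.

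Three stronger readings are tempting, and the documents support none of them.

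- **That the mTBI group is in fact enriched for milder cases, or cut off on the impaired side.** Section 8 requires a history of mTBI, not current symptoms, and Section 7 draws controls from people both affiliated and unaffiliated with the university. Nothing links tolerance to severity. Even under the model, imperfect correlation shifts the mean without removing the impaired tail.
- **That a patient who cannot perform the vergence task is necessarily dropped.** Section 14 speaks only of withdrawal. Vergence Pursuit is scored 0 to 100, so poor performance might simply be a low score.
- **That non-completion can never be known.** Section 14 does not forbid counting replaced subjects. It just does not require it.

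It is also fair to say that a worst-rank analysis is a matter of judgement. It treats every early stop as maximal impairment, so unrelated stops among mTBI patients would inflate the difference.

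**Conclusion.** The point holds in a conditional form. It is certain from the text that withdrawn subjects' data are discarded without exception for finished vergence recordings, that these subjects are replaced, and that SA2 and SA3 are therefore completers-only. It is also certain that stopping a test is not distinguished from withdrawing consent, and that no count by group is required.

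Whether this biases SA3 depends on withdrawals occurring, being related to symptoms, and being more common in the mTBI group. If so, the likely direction is toward no difference. Under the assumed model, for r between 0.3 and 0.8, the size runs from about 0.02 SD at 3% withdrawal to 0.28 SD at 20%. It is zero if nobody withdraws or if stopping is unrelated to vergence. The low end would hardly matter with 30 per group; the high end would cost substantial power.

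This is a worthwhile, inexpensive improvement to a stated rule. It is not evidence that the comparison is invalid.

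**What to change.** Reword Section 14 as follows:

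1. Distinguish stopping a test from withdrawing consent. Keep and analyse vergence and other test data recorded before a subject stops, unless the subject asks for their removal.
2. Replace a subject only if no vergence test was attempted. One who starts the vergence test and cannot finish it counts among the 30.
3. Report by group the number who started but did not complete the vergence test, with the test at which they stopped and the reason. Section 12 should list these items among the stored data.

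A rank-based sensitivity analysis of SA3, giving the worst rank to those unable to complete vergence testing, is optional. If it is used, it should be read alongside the recorded reasons for stopping.

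The cost is small, with no extra procedures. There may be slightly fewer than 30 complete vergence records per group, and some battery tests will have smaller denominators. The consent wording, which is not in the material reviewed, may need a matching change on the use of data already collected.
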